#### 10.4.1.2. ADVERSE EVENTS

Descriptive statistics (number and percent of eyes) will be presented for each MedDRA Preferred Term category of ocular adverse events and serious ocular adverse events reported, separately for first implanted eye, second implanted eye, and for both implanted eyes combined. Descriptive statistics (number and percent of subjects) will be presented for each MedDRA Preferred Term category of non-ocular adverse events and serious non-ocular adverse events reported. A listing of all adverse events and serious adverse events reported during the study will also be provided.

[figure not shown]

#### ***10.6. Handling of Missing Data***

All evaluable data will be used in the analyses; however, no imputation will be carried out for missing data.

#### ***10.7. Multiplicity***

No formal hypothesis testing is planned for any parameters and therefore no multiplicity adjustments are needed.

## **11. SAMPLE SIZE JUSTIFICATION**

[figure not shown]
The sample size will reflect the number of sites and subjects agreeing to participate.

All available and willing subjects meeting inclusion criteria will be included in the study (up to 778 subjects; up to 1321 eyes).

## 12. [REDACTED] ADVERSE EVENTS

### 12.1. *General Information*

#### **Definitions**

**Adverse Event (AE)** – any untoward medical occurrence, unintended disease or injury, or untoward clinical signs (including abnormal laboratory findings) in subjects, users or other persons, whether or not related to the investigational medical device. *Note: For subjects, this definition includes events related to the investigational medical device or the procedures involved. For users or other persons, this definition is restricted to events related to investigational medical devices.*

See Figure 12.1.-1 for categorization of adverse events.

**Adverse Device Effect (ADE)** – adverse event related to the use of an investigational medical device. *Note: This definition includes adverse events resulting from insufficient or inadequate instructions for use, deployment, implantation, installation, or operation; any malfunction; and use error or intentional misuse of the investigational medical device.*

**Nonserious Adverse Event** - adverse event that does not meet the criteria for a serious adverse event.

**Serious Adverse Event (SAE)** - adverse event that led to any of the following:

- Death.
- A serious deterioration in health that either resulted in:

- a) a life-threatening illness or injury.

*Note: Life-threatening means that the individual was at immediate risk of death from the event as it occurred, ie, it does not include an event which hypothetically might have caused death had it occurred in a more severe form.*

- b) any potentially sight-threatening event or permanent impairment to a body structure or a body function.
- c) in-patient hospitalization or prolonged hospitalization.

*Note: Planned hospitalization for a pre-existing condition, or a procedure required by the clinical investigation plan, without serious deterioration in health, is not considered a serious adverse event. In general, hospitalization signifies that the individual remained at the hospital or emergency ward for observation and/or treatment (usually involving an overnight stay) that would not have been appropriate in the physician's office or an out-patient setting. Complications that occur during hospitalization are adverse events. If a complication prolongs hospitalization or fulfills any other serious criteria, the event is serious. When in doubt as to whether "hospitalization" occurred, the event should be considered serious.*

- d) a medical or surgical intervention to prevent a) or b), or any ocular secondary intervention.
- e) any indirect harm as a consequence of incorrect diagnostic test results when used within manufacturer's instructions for use.

- Fetal distress, fetal death, or a congenital abnormality or birth defect.

[figure not shown]
See Figure 12.1.-2 for categorization of SAEs.

**Serious Adverse Device Effect (SADE)** – adverse device effect that has resulted in any of the consequences characteristic of a serious adverse event.

[figure not shown]
**Anticipated Serious Adverse Device Effect (ASADE)** – serious adverse device effect which by its nature, incidence, severity or outcome has been identified in the risk analysis.

**Unanticipated Serious Adverse Device Effect (USADE)** – serious adverse device effect which by its nature, incidence, severity or outcome has not been identified in the risk analysis.

**Figure 12.1.-1: Categorization of All Adverse Events**

**Figure 12.1.-2: Categorization of All Serious Adverse Events**

### **Specific Events Relevant to this Protocol**

In addition to reporting all adverse events (serious and non-serious) meeting the above definitions, the investigator must report any occurrence of the following serious adverse events as reported in the previous investigational protocols:

- Pupil ovalization >1 mm
- Hypopyon
- Intraocular infection/endophthalmitis
- Lens dislocation
- Macular edema (diagnosed clinically or confirmed by fluorescein angiography and/or optical coherence tomography)
- Pupillary block
- Hyphema
- Cataract formation
- Retinal detachment or retinal detachment repair
- Synechiae
- Corneal haze if associated with a loss of 2 lines or more (0.2 logMAR or more) of best corrected visual acuity (BCVA) from preoperative baseline
- Any secondary surgical intervention except retinal detachment repair (e.g., iridectomy for pupillary block, IOL repositioning, IOL removal due to inflammation, IOL replacement, and procedures that may be reported as “other”)
- Corneal stromal edema (Grade 3)
- Iritis (aqueous cells or flare of Grade 3 or higher)
- Raised IOP requiring treatment
- Loss of 2 lines or more (0.2 logMAR or more) of best spectacle-corrected visual acuity (BCVA) from preoperative baseline

Any other potentially sight-threatening events are also considered serious and have to be reported appropriately by the investigator as delineated in Section 12.2.

### **12.2. Procedures for Recording and Reporting**

All adverse events will be documented on the Adverse Event electronic case report form (eCRF) within the Electronic Data Capture (EDC) system and collected on a routine basis at monitoring visits. Adverse events must be collected from the time of informed consent.

In addition, the investigator must document all ADEs, SAEs, [REDACTED] with details including the date of occurrence, severity, treatment (if applicable), outcome, and assessments of the seriousness and causality. The site must submit all available information to the study sponsor immediately as follows:

- **ADEs or SAEs are documented on the *Adverse Device Effect and Serious Adverse Event Form* in the EDC system within 24 hours of the investigator's or site's awareness.**
- [REDACTED]  
[REDACTED]  
[REDACTED]
- **Additional relevant information after initial reporting is to be updated in the EDC system as soon as the data becomes available.**
- **Document any changes to the medical history and concomitant medication on the appropriate forms in the EDC system.**
- **All relevant documentation such as Discharge Summary, Autopsy Report, Certificate of Death etc, should be faxed to the study sponsor at [REDACTED].**

*Note:* Should the EDC system become non-operational, the site must complete the appropriate paper *Adverse Device Effect and Serious Adverse Event Form* [REDACTED]

[REDACTED] The completed form is faxed to the study sponsor at [REDACTED] within 24 hours of the investigator's or site's awareness; however, the reported information must be entered into the EDC system once it becomes available.

Study sponsor contact information is provided in Table 12.2.-1.

### **Intensity and Causality Assessments**

For every adverse event [REDACTED], the investigator must assess the causality as Related or Not Related to the medical device or test procedure in the study. An assessment of causality will also be performed by a study sponsor physician utilizing the same definitions, as shown below:

#### ***Causality***

Related An adverse event [REDACTED] classified as related may be either definitely related or possibly related where a direct cause and effect relationship with the medical device or test procedure has not been demonstrated, but there is a reasonable possibility that the adverse event [REDACTED] was caused by the medical device or test procedure.

Not Related An adverse event [REDACTED] classified as not related may either be definitely unrelated or simply unlikely to be related (ie, there are other more likely causes for the adverse event [REDACTED]).

Where appropriate, the investigator must assess the intensity (severity) of the adverse event as mild, moderate, or severe based on medical judgment with consideration of any subjective symptom(s), as defined below:

***Intensity (Severity)***

Mild	An adverse event is mild if the subject is aware of but can easily tolerate the sign or symptom.
Moderate	An adverse event is moderate if the sign or symptom results in discomfort significant enough to cause interference with the subject's usual activities.
Severe	An adverse event is severe if the sign or symptom is incapacitating and results in the subject's inability to work or engage in their usual activities.

***12.3. Unmasking of Study Information***

Not applicable; this study is open-label.

***12.4. Follow-Up of Safety Information***

The investigator is responsible for adequate and safe medical care of subjects during the study and for ensuring that appropriate medical care and relevant follow-up procedures are maintained after the study. The investigator should provide the sponsor with any new safety information (which includes new adverse events and changes to previously reported adverse events) that may affect the safety evaluation of the device. Any additional data from these follow-up procedures performed up to 6 months after subject exit must be documented and available upon the study sponsor's request.

### **13. REGULATORY AND ETHICAL COMPLIANCE**

This clinical trial will be conducted in accordance with the principles of the Declaration of Helsinki, and in compliance with ISO 14155:2011 clinical investigation of medical devices for human subjects, Good Clinical Practice (GCP), Code of Federal Regulations (CFR), Standard Operating Procedures (SOPs) of Alcon and Contract Research Organizations participating in the conduct of the clinical trial, and all other applicable regulations.

### **14. RESPONSIBILITIES**

#### ***14.1. Investigator Responsibilities***

The Investigator will comply with the commitments outlined in the Statement of Investigator (Form FDA 1572 or Alcon Form CS006). The Investigator and all clinical trial staff will conduct the clinical trial in compliance with this protocol and with GCP and all applicable regulatory requirements. The Investigator will ensure that all personnel involved in the conduct of the clinical trial are qualified to perform their assigned duties through relevant education, training, and experience.

#### ***14.2. Sponsor and Monitor Responsibilities***

The Sponsor will designate a monitor to conduct the appropriate site visits at the appropriate intervals. The clinical investigation will be monitored, following the Monitoring Plan, to ensure that: the rights and well being of the patients are protected; the reported data are accurate, complete, and verifiable from the source documents; the equipment used to assess variables in the clinical investigation is maintained and calibrated per manufacturer instructions and Sponsor requirements; the study is conducted in compliance with the current approved protocol (and amendment[s], if applicable), with current Good Clinical Practice (GCP), and with applicable regulatory requirements.

All studies will have a site initiation. Monitoring will be conducted periodically while the clinical study is ongoing. Monitoring methods may include site visits, telephone, written and fax correspondence. The Study Manager and/or the assigned Clinical Site Manager will contact each site at appropriate intervals. The Lead Clinical Site Manager will determine the frequency of site visits. Close-out visits will take place after the last visit of the last patient.

## 17. STUDY PLAN

**Table 17.-1:**  
**Study Plan**

Procedure / Assessment	Entrance Visit a	Nominal Time ± Visit Window Limits												
		Day 1429 – 1550	Day 1794 – 1915	Year 4/4A c	Year 5/5A d	Year 5.5/5.5A	Year 6/6A	Year 6.5/6.5A	Year 7/7A	Year 7.5/7.5A	Year 8/8A	Year 8.5/8.5A	Year 9/9A	Year 9.5/9.5A
Informed Consent	X				Day 1976 – 2097	Year 5.5/5.5A								
Inclusion/Exclusion	X				Day 2159 – 2280		Year 6/6A							
Enrollment Information e	X				Day 2341 – 2462	Year 6.5/6.5A								
Medical History	X				Day 2524 – 2645	Year 7/7A								
Central [REDACTED] [REDACTED] T Endothelial Cell Photography-3 images each		X	X	X	X	X	X	X	X	X	X	X	X	X

Adverse Events

(both volunteered  
and elicited)

X X X X X X X X X X X X

aThe subject's initial C-09-043 study examination may be Year 4 or later (i.e., Year 4, 5, 5.5, 6, etc.). Point of entry is determined by each subject's eye surgery date and the next available visit listed here to enable continued yearly examination. As in previous studies, subjects with the ACRYSOF CACHET Phakic Lens (L-Series) implanted in both eyes will have separate study visits, as needed, for each eye to capture the data within the window of the annual implant date anniversary.

bStudy Day is relative to the surgery date for each implanted eye.

[figure not shown]
cData from subject's 2nd implant surgery will be captured on Forms designated with an "A".

[figure not shown]
dA 4.5 Year visit is not included since all patients are past this time-point.

[figure not shown]
eThe Enrollment Information panel will collect basic information from the subject's previous study (e.g., protocol number, investigator number, subject number, and the first Form/Visit where data is captured in this study for each eye).

[figure not shown]

[figure not shown]

[figure not shown]

**Job Notes:**

C-09-043 is the extended safety follow-up study for subjects previously implanted with the AcrySof® CACHET® Phakic Lens (L-series) in clinical studies C-02-23, C-02-40, C-03-21 and C-05-57.

**Summary:****Evaluability**

All subjects enrolled in the study will be considered evaluable for the safety analysis.

**Analysis**

[figure not shown]
[figure not shown]
The primary objective is to estimate the annualized endothelial cell loss rate (for up to 10 years following date of implantation) of subjects previously implanted with the AcrySof® CACHET® Phakic Lens (L-Series) from clinical studies C-02-23, C-02-40, C-03-21 and C-05-57.

The secondary objective is to collect additional safety data that may identify risk factors for eyes with significant endothelial cell loss.

**Safety Variables and Assessments**

[figure not shown]
The safety parameters include:

- Central Endothelial Cell Density
- Adverse Events

## 1. STUDY SUMMARY

Study Phase:	Not applicable – Study is observational only
Test Article(s) / Product(s):	AcrySof® CACHET® Phakic Lens (L-Series)
Study Dosage / Usage:	Intraocular lenses are implantable medical devices and are intended for long term use over the lifetime of the subject. The phakic intraocular lens may be removed as needed (e.g. cataract extraction).
Route of Administration:	Not applicable
Objective(s):	
The primary objective is to estimate the annualized endothelial cell loss rate (for up to 10 years following date of implantation) of subjects previously implanted with the AcrySof® CACHET® Phakic Lens (L-Series) from clinical studies C-02-23, C-02-40, C-03-21 and C-05-57.
 
The secondary objective is to collect additional safety data that may identify risk factors for eyes with significant endothelial cell loss.

Study Population:	Subjects previously implanted with the AcrySof® CACHET® Phakic Lens (L-series) in clinical studies C-02-23, C-02-40, C-03-21 and C-05-57 (includes subjects who have had the lens explanted for any reason).

Structure:  Parallel Group   Duration of Treatment:  
 Duration of Assessment:

Crossover   Number of Treatments:  
 Number of Sequences:  
 Number of Periods:  
 Duration of Periods:  
 Washout Between    Yes    No  
 Periods:

Other   No control, open label study  
 Duration of Treatment: Subjects to be followed for 5 to 7 years (10 years from the time of implantation).

[figure not shown]
Multi-center:  Yes   Number of Centers: Up to 35  
 No

Masking:  None Observer-Masked Patient-Masked Double-MaskedRandomization:  Yes Group Assignment Ratio: NoConcurrent  NoneControl:  No Treatment Placebo Active Specify: Other Specify:Estimated Total Sample Size: Required: N/A  
Planned: Up to 1321 eyes

Safety Primary Safety

Variable(s):

- Central endothelial cell density
- Adverse Events

[figure not shown]
[figure not shown]
Adverse Events:  Both volunteered and elicited Other:

## 2. SAFETY VARIABLES

### 2.1. *Description*

The safety of the AcrySof® CACHET® Phakic Lens (L-Series) will be assessed for the following safety parameters:

- Central Endothelial Cell Density
- Adverse Events

## 2.2. Measurement Time

**Table 2.2-1: Study Plan**

Procedure / Assessment	Central	Nominal Time ± Visit Window Limits											
		Year Visit a	Year 4/4A c	Year 5/5A	Year 5.5/5.5A	Year 6/6A	Year 6.5/6.5A	Year 7/7A	Year 7.5/7.5A	Year 8/8A	Year 8.5/8.5A	Year 9/9A	Year 9.5/9.5A
Procedure / Assessment													
Central	ECD												
Adverse Events													

a The subject's initial C-09-043 study examination may be Form 9 or later (i.e., Form 9, 10, 11, etc.). Point of entry is determined by each subject's eye surgery date and the next available visit listed here to enable continued yearly examination. As in previous studies, subjects with the AcrySof® CACHET® Phakic Lens (L-Series) implanted in both eyes will have separate study visits, as needed, for each eye to capture the data within the window of the annual implant date anniversary.

b Study Day is relative to the surgery date for each implanted eye.

c Data from subject's 2nd implant surgery will be captured on Forms designated with an "A".

### ***2.3. Unit of Analysis***

The eye will be the unit of analysis for all safety parameters except for non-ocular adverse events where the unit of analysis will be subject.

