#### **10.4.1. PRIMARY SAFETY**

##### **10.4.1.1. CENTRAL ENDOTHELIAL CELL DENSITY**

Descriptive statistics for central endothelial cell density, for each scheduled visit (including data from previous studies), will be provided. Descriptive statistics for central endothelial cell density chronic change (actual and percent) from baseline (6 month visit in previous study) to each scheduled visit will be provided. Descriptive statistics for central endothelial cell density change (actual and percent) between consecutive scheduled visits will be provided. All tables will be generated separately for first implanted eye, second implanted eye, and for both implanted eyes combined. Descriptive statistics include mean, median, standard deviation, sample size, minimum, maximum and confidence limits.

The mean rate of endothelial cell density decrease will be calculated via a paired analysis in order to calculate the mean of the differences between each reporting period.

[figure not shown]

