### ***2.4. Descriptive Statistics***

Descriptive statistics for both eyes combined will be provided for endothelial cell density and adverse events. The statistics presented for continuous variables will include mean, median, standard deviation, number of eyes, minimum and maximum. The statistics for categorical variables will include sample size and percentage in the categories.

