##### 4.1.2.1. CHRONIC CHANGE FROM DAY 147-182 (MONTH 6 IN PREVIOUS STUDIES)

[figure not shown]
Descriptive statistics will be provided for each scheduled visit, for [REDACTED] central [REDACTED] endothelial cell density, for all eyes combined. The statistics presented for endothelial cell density (using the average from the analyzable images for each eye) will include mean, median, standard deviation, sample size, minimum, and maximum.

[figure not shown]
The percent change of mean endothelial cell density over time from Day 147-182 (Form 5 or 5A) in the previous studies to each visit in the current study will be calculated. The actual and annualized percent change of mean endothelial cell density from the Day 147-182 (Form 5 or 5A) exam to each scheduled visit in this study will be calculated and presented along with median, standard deviation, sample size, minimum and maximum. Tables presenting the mean, median, standard deviation, sample size, minimum and maximum of baseline (Form 5 or 5A in previous studies) endothelial cell density and cell density change from baseline to each scheduled visit in this study will be presented for all eyes combined.

[figure not shown]

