### **4.2.2. ADVERSE EVENT ANALYSIS**

Adverse events will be coded with MedDRA Preferred Term codes. Descriptive statistics (number and percent of eyes) will be presented for each MedDRA Preferred Term category of ocular adverse events and serious ocular adverse events reported, separately for first

implanted eye, second implanted eye and both eyes combined. Separate tables will be generated for AEs, SAEs, and ADEs. Descriptive statistics (number and percent of subjects) will be presented for each MedDRA Preferred Term category and System Organ Class of non-ocular adverse events and serious non-ocular adverse events reported. In addition, a one-sided upper 95% confidence interval on the percent of each MedDRA Preferred Term code will be calculated

A listing of all adverse events and serious adverse events including investigator, subject number, onset day, eye, lens model, causality assessment, severity, outcome and the MedDRA Preferred Term code for the adverse event will also be provided.

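### Combined-eye confidence limits have no visible provision for fellow-eye correlation; computed on the eye count, they would be too narrow

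*SAP*

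**What the plan says.** SAP 2.3 sets the unit: "The eye will be the unit of analysis for all safety parameters except for non-ocular adverse events", for which it is the subject. Cell density and ocular adverse events are therefore counted by eye.

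Confidence limits appear in two places.

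- **Adverse events.** SAP 4.2.2 tabulates ocular terms as a percent of eyes, for first eye, second eye and both eyes combined. It then says that "a one-sided upper 95% confidence interval on the percent of each MedDRA Preferred Term code will be calculated". That sentence follows the text on non-ocular events and names no column. Its reference to each Preferred Term most naturally takes in the ocular terms.
- **Cell density.** Protocol 10.4.1.1 says "All tables will be generated separately for first implanted eye, second implanted eye, and for both implanted eyes combined" and "Descriptive statistics include mean, median, standard deviation, sample size, minimum, maximum and confidence limits". The SAP lists are shorter. Section 2.4 reads "The statistics presented for continuous variables will include mean, median, standard deviation, number of eyes, minimum and maximum", and for density at each visit section 4.1.2.1 says the statistics "will include mean, median, standard deviation, sample size, minimum, and maximum". Section 4.1.2.2 gives the same list. None of the three includes confidence limits, and all present density for all eyes combined.

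The sample, in protocol section 11, is "up to 778 subjects; up to 1321 eyes". Protocol 7.1 admits subjects implanted in one eye or both. Protocol 10.7 plans no hypothesis tests.

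Neither document visibly gives an interval method, a clustered or robust variance, a mixed model for these limits, or any statement about fellow eyes. Parts of both analysis sections are redacted, so this describes the visible text only.

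**The concern.** Two eyes of one person share age, ocular biology and, here, the same lens design, so their outcomes are likely to be positively correlated. A variance that divides by the number of eyes ignores this and overstates the information in a combined-eye table. Naming the eye as the unit, with no interval method given, points a programmer to exactly that calculation.

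Because the study tests nothing, its confidence limits are the planned statement of precision. For an ocular adverse event the planned limit is an upper safety bound, and ignoring the correlation makes that bound too low.

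**Working it through.** The plan has no precision calculation to reproduce. Protocol section 11 lets the sample reflect who agrees to take part.

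**Inputs from the documents:** at most 778 subjects and 1321 eyes (protocol section 11). **Assumptions:** every subject contributes at least one eye; enrolment reaches the ceilings; fellow-eye correlation rho is 0.1, 0.3, 0.5 or 0.8, because the documents give no value; density limits are two-sided 95%, because the protocol gives no level.

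**Step 1, pairing.** Bilateral subjects: 1321 − 778 = 543. Unilateral subjects: 778 − 543 = 235. Check: 235 + 2 × 543 = 1321. Share of eyes with a fellow study eye: 1086/1321 = 0.822.

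**Step 2, design effect.** With m eyes per subject, Σm²/Σm = (4 × 543 + 235)/1321 = 1.822. The variance of a combined-eye mean or proportion, relative to independence, is therefore DE = 1 + 0.822 × rho. The correct interval is √DE times as wide, and the effective number of eyes is 1321/DE.

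**Step 3, coverage of a two-sided 95% interval for mean density computed on 1321 eyes:** 2Φ(1.96/√DE) − 1.

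| rho | DE | Correct interval wider by | Effective eyes | Actual coverage |
|---|---|---|---|---|
| 0.1 | 1.08 | 4% | 1221 | 94.0% |
| 0.3 | 1.25 | 12% | 1060 | 92.1% |
| 0.5 | 1.41 | 19% | 936 | 90.1% |
| 0.8 | 1.66 | 29% | 797 | 87.2% |

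Simulating the density case with 20,000 runs gave 89.8% at rho 0.5 and 87.0% at rho 0.8, in line with the formula.

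**Step 4, one-sided upper 95% limit for an ocular event.** I took the Clopper-Pearson limit at an observed rate p, first with n = 1321 and then with n = 1321/DE.

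| Observed rate | On eye count | rho 0.1 | rho 0.3 | rho 0.5 | rho 0.8 |
|---|---|---|---|---|---|
| 1% | 1.58% | 1.61% | 1.67% | 1.72% | 1.80% |
| 3% | 3.89% | 3.93% | 4.01% | 4.09% | 4.20% |

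The 1% row uses 13.21 events (0.01 × 1321). With 13 whole events the eye-count limit is 1.56%.

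**Step 5, coverage of the eye-count upper limit.** This was simulated with 200,000 replicates: 543 pairs with P(both eyes) = p² + rho·p(1 − p), plus 235 single eyes.

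| True rate | rho 0.1 | rho 0.3 | rho 0.5 | rho 0.8 |
|---|---|---|---|---|
| 1% | 94.6% | 93.2% | 91.8% | 89.9% |
| 3% | 94.7% | 93.4% | 92.1% | 90.1% |

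At rho 0 the 1% event has 95.3% coverage. A repeat with another random seed agreed within 0.2 percentage points.

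**Step 6, by-eye comparison.** Taking 778 first eyes and 543 second eyes, the upper limits for a 1% event are 1.81% and 2.03%. These have one eye per subject and so no pairing problem.

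**The case against.** The strongest reply is that nothing visible turns on this. There is no test, no acceptance limit is compared with an interval, and the 1% bound moves by at most about 0.2 percentage points. That is true, and it keeps the point from being critical.

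Naming the eye as the unit does not itself prescribe an independence variance, since a mixed model also has eyes as its observations. That is right, and the finding is conditional for this reason. But with no interval method visible, the unit rule is the only guidance a programmer has.

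For density, the SAP lists no confidence limits. If the SAP governs, no density interval is affected, and what remains is a mismatch with the protocol. For adverse events, the sentence in 4.2.2 follows the non-ocular text, so applying it to the combined ocular column is a reading, though the natural one. Redacted entries in the density part of the SAP and in the protocol's analysis section could hold a suitable method. The adverse event analysis text itself shows no redaction.

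The size is also uncertain. One correlation range serves both a continuous measure and rare events, and for a 1% event rho 0.8 would mean that about 80% of affected eyes have an affected fellow, so the upper end is an extreme for events. The exact limit is conservative for very rare terms: with no events in 1321 eyes it is 0.227%, so any term with a true rate below that is always covered. At rho 0.1, coverage is close to nominal. The 82% paired share applies at the ceilings; density sets at each visit will be smaller because of missed visits and excluded post-explantation data.

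These points limit the size and the certainty. They do not supply the missing provision.

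**Conclusion.** The concern holds for the visible text. Both-eyes-combined limits computed on the eye count are too narrow if fellow eyes are positively correlated, and for ocular events the error is in the unsafe direction. At moderate to high assumed correlation (0.5 to 0.8), a limit labelled 95% would cover about 90% to 92% for 1% and 3% events, and about 87% to 90% for mean density. The absolute shift in an event bound is small. Means, percentages, and first-eye or second-eye limits are not affected.

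The result rests on the assumed correlation, on enrolment at the ceilings, and on no redacted section already dealing with the matter. It should be fixed, but it does not threaten the study's conclusions.

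**What to change.** 1. In SAP 2.3 and 4.2.2, state that every both-eyes-combined limit on an ocular event percent treats the subject as the cluster, using a subject-level bootstrap or a cluster-adjusted exact limit.
2. In SAP 4.2.2, say that the one-sided limit applies to ocular terms, and in which columns: first eye, second eye, combined.
3. Reconcile SAP 2.4, 4.1.2.1 and 4.1.2.2 with protocol 10.4.1.1 on whether density tables carry confidence limits. If they do, compute the combined-eye limits with a subject-clustered robust variance or a mixed model with a subject random effect.
4. If a redacted section already covers this, a cross-reference in SAP 2.3 is enough.

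Point estimates stay per eye, and limits in by-eye tables need no adjustment. The cost is a few sentences and a standard program option, with combined-eye intervals about 4% to 29% wider over the assumed range. Data collection does not change.
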